3.6.10. Primary safety endpoints

As FS is approved for the intravenous injection for ophthalmological applications and the safety profiles are well characterized and considered low risk. As described above the most common side effects are nausea and vomiting. This side effect is commonly experienced with resection of vestibular schwannoma due to transection of the vestibular nerve and resulting vertigo. Thus, this side effect will not be tracked or reported. Other adverse effects of SF—urticaria, anaphylaxis, seizure, cardiac events, respiratory compromise—will be tracked and reported up to 3 months after surgery. The relevance of the adverse event to the administration of SF will be determined by the principal investigator.

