Intraoperative fluorescence imaging has been utilized in the resection of HNP and meningiomas. Indocyaninegreen fluorescence angiography has been used to assess post-embolization vascularity of paraganglioma to estimate bleeding risk.⁸ FS has been utilized with the YE560 to distinguish meningioma and hyperostosis from surrounding brain and healthy bone.⁹

FS is FDA approved for ophthalmologic applications. The standard dose for retinal imaging in adults is a 500 mg bolus into a peripheral vein (7.1 mg/kg in a 70 kg patient).¹⁰ The safety profile of intravenous FS is well-described in the ophthalmology literature. Nausea and vomiting are the most common side effect reported, but 87% of surveyed ophthalmologists reported rates less than 5%. Urticaria is estimated to occur at a rate of 1 in 82 patients. Severe adverse reactions, including respiratory reactions (1:3,800), cardiac events (1:5300), and tonic-clonic seizure (1:13,900) are rare and estimated to occur cumulatively in 1 in 1900 patients.¹¹

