3.6.5. Inclusion Criteria

Inclusion criteria shall be:

- Patient with a suspected VS, meningioma, HNP or HNS
- Recurrent VS, meningioma, HNP, or HNS with prior microsurgical resection or radiation therapy
- Clinical indication for microsurgical resection

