7.4. Subject Compliance and Adverse Event Monitoring

7.4.1. Adverse Event Monitoring

Adverse events (AEs) must be reported on the Adverse Event Form (AEF). Adverse events that will be monitored include urticaria, anaphylaxis, respiratory compromise, cardiac events, seizure, and death. These events will be monitored in the first 3 months after surgery. Complete clearance of SF is expected within 72 hours, and associated adverse events, if any, are anticipated within that timeframe. After discharge from the hospital, any reporting of adverse events will rely upon participants contacting the research team prior to the scheduled 3 month follow up. Nausea and vomiting will not be included as an adverse event as these symptoms are expected outcomes from surgery.

If adverse events occur, the first concern will be the safety and welfare of the patient. Appropriate medical intervention will be made. Any adverse events observed by the Investigator or reported by the patients will be recorded in the appropriate section of the patient's Case Report Form (CRF) as well as on an Adverse Event Form.

The Investigator must categorize each AE by degree of harm to the patient (mild, moderate, or serious), and the relationship to study device (not related, possibly, probably, or definitely) in the Adverse Event Form. Adverse events observed will be captured on the Adverse Event Follow-up Form and the CRF until such time the adverse event is reported as resolved, or for the course of the study if the event does not resolve.

A serious adverse event includes any prolong hospitalization, and any event that is life-threatening, results in permanent impairment of a bodily function or permanent damage to a body structure, or an event that necessitates medical or surgical intervention to preclude such permanent impairment or permanent damage.

Changes in any chronic condition or disease that are consistent with natural disease progression are not considered AEs and will not be recorded on an AE CRF.

Medical treatment related to any adverse events will not be paid for by the study, Mayo Clinic, or the Sponsor. Patients and their insurance will be billed for any treatments or encounters associated with an adverse event.

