7.4.2. Adverse Event Reporting

Any serious adverse events, whether unanticipated or not, and whether or not ascribed to study device, will be communicated promptly to Carl Zeiss Meditec Inc and to the IRB. These reports must be confirmed in writing within 5 days of the occurrence.

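### Nausea and vomiting go untracked in all patients for a reason specific to vestibular schwannoma surgery, and calling them non-events conflicts with the serious-event rules in 7.4.1 and 7.4.2

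*Protocol*

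**What the plan says.** Section 3.6.10 (Primary safety endpoints) states: "As described above the most common side effects are nausea and vomiting". It then gives its reason for setting them aside: "This side effect is commonly experienced with resection of vestibular schwannoma due to transection of the vestibular nerve and resulting vertigo". It concludes: "Thus, this side effect will not be tracked or reported". No limit by tumor type is attached.

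Section 7.4.1 (Adverse Event Monitoring) applies the same exclusion on a different ground: "Nausea and vomiting will not be included as an adverse event as these symptoms are expected outcomes from surgery". Its list of monitored events is urticaria, anaphylaxis, respiratory compromise, cardiac events, seizure and death. The same section says of seriousness: "A serious adverse event includes any prolong hospitalization". Section 7.4.2 sets the scope of reporting to the sponsor and the IRB: "Any serious adverse events, whether unanticipated or not, and whether or not ascribed to study device".

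The first inclusion criterion in section 3.6.5 reads: "Patient with a suspected VS, meningioma, HNP or HNS". Section 3.5 plans 90 patients across these tumor types and gives no split.

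The only frequency for the excluded symptoms is in section 3.2: "Nausea and vomiting are the most common side effect reported, but 87% of surveyed ophthalmologists reported rates less than 5" percent.

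**The concern.** There are two separate problems.

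First, the reason in 3.6.10 is narrower than the rule it supports. Transection of the vestibular nerve is offered as the cause of nausea after vestibular schwannoma (VS) resection. Nothing in 3.6.10 extends that to meningioma, head and neck paraganglioma (HNP) or head and neck schwannoma (HNS), yet their symptoms go unrecorded too. The final report could then give no rate for the dye's most common side effect in those patients. A statistical analysis plan cannot repair this, because the data would not have been collected.

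Second, being expected is the ground for exclusion in 7.4.1, but 7.4.2 does not accept it as a ground for not reporting a serious event. Vomiting that prolongs a hospital stay is not an adverse event under one sentence and is reportable under others. Site staff could follow either, and one path leaves a serious event unreported. This applies to every tumor type, VS included.

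**Working it through.** **Step 1: the reasons side by side.**

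| Section | Reason given | Patients the reason covers | Patients the rule covers |
|---|---|---|---|
| 3.6.10 | Vestibular nerve transection and vertigo | VS resections | All |
| 7.4.1 | Symptoms expected from surgery | All, by assertion | All |
| 3.6.5 (enrollment) | not applicable | not applicable | VS, meningioma, HNP, HNS |

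The 3.6.10 reason leaves three enrolled tumor types uncovered. The 7.4.1 reason covers them in words, but with no rate or source for those operations.

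**Step 2: the serious-event chain.** Take vomiting that prolongs hospitalization.
- By the exclusion sentence in 7.4.1, it is not an adverse event.
- By the serious-event definition in 7.4.1, a prolonged hospitalization is serious.
- By 7.4.2, a serious event is reported whether or not it was anticipated and whether or not it is attributed to the device.

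The first statement and the last two give opposite instructions, and the protocol does not say which takes precedence.

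**Step 3: scale.** Inputs from section 3.2 are urticaria at 1 in 82, severe reactions at 1 in 1900, and nausea or vomiting below 5% according to 87% of respondents. From section 3.5, n = 90. The severe figure agrees with its parts: 1/3800 + 1/5300 + 1/13,900 = 1/1909, close to the stated 1 in 1900.

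Expected events are n × p. The chance of at least one is 1 − (1 − p)^n.

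| Event | Rate | Expected in 90 | Chance of at least one |
|---|---|---|---|
| Nausea or vomiting, upper figure | 5% | 90 × 0.05 = 4.5 | 99% |
| Nausea or vomiting, assumed | 2% | 90 × 0.02 = 1.8 | 84% |
| Nausea or vomiting, assumed | 1% | 90 × 0.01 = 0.9 | 60% |
| Urticaria | 1/82 | 90/82 = 1.1 | 67% |
| Severe reactions | 1/1900 | 90/1900 = 0.05 | 4.6% |

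The untracked symptoms as a share of all expected dye events:
- At 5%: 4.5/(4.5 + 1.10 + 0.05) = 80%.
- At 2%: 1.8/(1.8 + 1.10 + 0.05) = 61%.
- At 1%: 0.9/(0.9 + 1.10 + 0.05) = 44%.

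**Step 4: patients outside VS.** Their number is not stated. Assuming 15 to 60 of them and a rate of 1% to 5%, the expected dye-related count runs from 15 × 0.01 = 0.15 to 60 × 0.05 = 3.0. The chance of at least one runs from 14% to 95%.

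**The case against.** The strongest reply is that the exclusion does not rest on VS alone. Section 7.4.1 gives a reason for all patients, and section 3.6.11 has all of them under anesthesia for a craniotomy or a translabyrinthine approach. This stands in part: 3.6.10 is not the protocol's only rationale. But the broader reason is asserted rather than supported, and the two sections should agree.

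A reader might infer that the surgical cause of nausea is absent in the other tumor types. The protocol does not say so. Section 1.3 places those tumors next to cranial nerves and is silent on vestibular effects. The claim is only that the stated reason does not address them.

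A reader might also infer that nausea and vomiting are the only dye effect likely to be seen. Urticaria is tracked and has about a 67% chance of appearing at least once. The 80% share depends on using 5% as the rate, and it falls to 61% or 44% at 2% or 1%.

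A third tempting inference is that a dose-tolerability signal is being lost. The dose objective in section 3.1 is judged from surgeon surveys, section 3.6.11 aims to standardize the dose after 10 cases, and there is no control group. Between 0.15 and 3.0 expected events, mixed with background postoperative nausea, could not show a dose relation.

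On serious events, it can be argued that a prolonged stay is reportable in itself, so the exclusion reaches only the routine symptom. That reading is reasonable, but the text does not state it, and a blanket statement that the symptoms are not adverse events invites the opposite one.

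Finally, the protocol openly explains its choice, for an approved dye in a largely descriptive study. That argues for a modest change, not for none. For the events it does track, 3.6.10 leaves relevance to FS to the principal investigator, so uncertain attribution is not otherwise treated as a reason not to record.

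**Conclusion.** The point holds in two parts. The exclusion in 3.6.10 is wider than its reason, and 7.4.1 supplies a different, unsupported one. The rule that nausea and vomiting are not adverse events also contradicts the serious-event definition in 7.4.1 and the reporting duty in 7.4.2. The second part needs no assumption about rates or case mix.

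The size is modest: about 4.5 events in 90 patients at 5%, and 0.9 to 1.8 at 1% to 2%. This assumes that rates from retinal imaging carry over to anesthetized patients who start at a lower dose: section 3.2 gives 500 mg, or 7.1 mg/kg at 70 kg, for imaging, and section 3.6.11 starts at 1 mg/kg. Section 3.2 gives no mean rate and does not describe the other 13% of respondents, so 4.5 is an upper figure only if 5% is accepted as one.

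Unrecorded here means not collected as study data; hospital notes may still hold the symptoms. The sponsor should correct this, but it does not threaten the primary endpoint.

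**What to change.** Reconcile 3.6.10, 7.4.1 and 7.4.2 as follows.

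1. Limit the exclusion in 3.6.10 and 7.4.1 to non-serious nausea and vomiting in VS resections.
2. State that nausea or vomiting meeting the serious definition in 7.4.1 is reported under 7.4.2 in every tumor type.
3. In meningioma, HNP and HNS patients, record nausea and vomiting from the inpatient record within the 72-hour clearance window that 7.4.1 already states, together with the cumulative FS dose. Tabulate the counts descriptively by tumor type.

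The cost is protocol wording and entries on existing forms. Once these symptoms count as adverse events outside VS, the 7.4.1 requirements for severity grade, relationship and follow-up apply to each entry, so the work is more than a single tick box. The number of entries depends on a background nausea rate that the protocol does not give. The counts will include ordinary postoperative nausea and, with non-serious events in VS still excluded, will have no full VS rate beside them. They support a descriptive rate only, not attribution to FS or a dose-response conclusion, and the report should say so.

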3.6.11. Microscope imaging during YE560 fluorescence use

1. Standard methods of anesthesia as appropriate for open craniotomy or otologic surgery will be used.
2. Surgeons will gain access to the lesion of interest through a craniotomy or translabyrinthine approach.

3. At the time of tumor exposure, patients will be given intravenous FS. The timing and dose may vary. Maximum cumulative dose will not exceed 500 mg.

- Initial dosing protocol will be 1 mg/kg intravenous FS.
 - If insufficient fluorescence is obtained or washout occurs, additional doses of 1 mg/kg may be administered
- Based on the experience of the first 3 cases, modifications to the dosing protocol may be made.
 - A higher, single dose may be administered if there is insufficient fluorescence or premature washout. Additional doses may be given during surgery.
 - If saturation of normal tissue with fluorescence occurs, the dose may be decreased or the FS may be administered at an earlier time point (opening of dura, anesthesia induction, etc.) during subsequent cases
- Continued adjustments may be made to the dosing and timing, with a goal of standardizing the dose after 10 cases

4. Once the VS has been surgically exposed and FS has been administered, the YE560 fluorescence module shall be used to visualize fluorescence in the tissue. Images will be captured prior to tumor dissection, after exposure of the intracapsular tumor contents, and after maximum resection. A pair of images—one using the YE560 and one with white light microscopy—will be captured during each event.

5. With the YE560 turned on, images will be captured with the microscope. Video recording from the Pentero 900 and Kinevo 900 microscopes will be captured for the entirety of their use in the case.

6. The time from injection until to the point where the differential fluorescence is greatest will be recorded and documented in the surgeon's survey. Circulating nursing staff will record timestamps in collaboration with instruction from the operating surgeons.

7. The YE560 module will be applied during the aforementioned events and additionally at the discretion of the operating surgeons. Depending upon the number of potential regions identified for imaging and for possible biopsies, the YE560 fluorescence module is expected to add less than 10 minutes to the overall procedure.

8. At any time, the operating surgeon may turn off the YE560 module as dictated by the needs of surgery.

9. Following completion of tumor resection and prior to closing of the dura, supramaximal and minimum stimulation values will be obtained (if relevant), as is standard practice with vestibular schwannoma microsurgery at our institution. The process is as described in Schmitt et al. (2013). In brief, transcutaneous bipolar electrodes are used at the extratemporal main trunk of the facial nerve to stimulate the nerve at 100 msec pulses increasing from 0 mA until a plateau amplitude compound muscle action potential is obtained. A Prass probe is used to stimulate the facial nerve proximal to the tumor (at the brainstem if possible) at increasing current (starting at 0 mA) until a plateau of CMAP is obtained. The ratio of these amplitude responses is calculated and subtracted from 1 to calculate the supramaximal stimulation. The minimum stimulation is the minimum current level at which a reliable facian nerve response can be obtained with proximal stimulation of the facial nerve using the Prass probe.

11. Suspected lesions that are found to be a histopathological entity excluded from this study after microsurgical resection and biopsy will be withdrawn from the study.

12. Post-procedure data analysis will include analysis of surgeon survey responses and, red/green/blue component analysis using ImageJ software. Additional data (demographics, imaging characteristics, facial nerve and audiometric data) will be reviewed and recorded from preoperative and 3 month postoperative visits. Video recordings will be edited to 30-60 second videos following the case with

representative views of the VS, facial nerve and cochlear nerve with and without the YE560 active. These edited videos will be used for the aforementioned surgeon validation study rating the correlation of fluorescence with white light microscopy.

13. Upon completion of surgery, operating surgeons will complete the remainder of the paper survey (Appendix 3). The surveys will be collected, with responses logged in the Rave database. The paper surveys will be stored in a secure location in the Otolaryngology department.

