3.4. Hypothesis

12. Given prior evidence of preferential uptake of FS in VS and meningiomas due to disrupted blood brain barrier, we hypothesize that use of intravenous FS will allow for visual differentiation of tumor and surrounding structures and nerves using YE560.
13. The optimal dosing for FS has not been established for this application. Pedro et al utilized 0.5-1.0 mg/kg body weight to visualize peripheral nerve sheath tumors with YE560. The authors found saturation of all tissues with 3-4 mg/kg dose within 18 seconds of administration. The blood-brain barrier may play a modulating role. Schebesch et al (2013) used 3-4 mg/kg to visualize malignant gliomas and observed fluorescence after 20-30 minutes. We suspect that the optimal dose will be 3-4 mg/kg, and peak fluorescence will take a similar amount of time. However, we will initially utilize 1.0 mg/kg SF administered at the time of first visualizing the tumor to enable subsequent doses (up to a maximum of 500 mg or 7 mg/kg). This will allow us

to determine the minimum effective dose and observe the time to peak fluorescence. The optimal dosing strategy will be finalized after the first 10 cases.

14. We hypothesize that the surgeons will be satisfied with the use of SF and YE560, as reflected in responses on the Surgeon Survey. Specifically, we hypothesize that greater than 75% of surgeons would choose to use SF and YE560 at least in the majority of future VS, meningioma, HNP, or HNS resections based on responses from the Surgeon Survey. Secondarily, we hypothesize that surgeons will rate the correlation of fluorescence with visual assessment with white light microscopy and electrostimulation to be “good” or “excellent” for over 75% of the cases.
15. Because the yellow fluorescence is primarily comprised of red and green components, we hypothesize that RGB component analysis of intraoperative images will yield significantly higher red and green values in the VS compared to the facial and cochlear nerves. Similar analysis may be conducted between the tumor and surround nerves or structures of interest for meningiomas, HNP, and HNS.

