1. Fluorescein Sodium Administered: _____ ; corresponding event (e.g. opening dura): _____
 - a. If second dose given, time administered: _____, dose _____ mg/kg
 - b. If third dose given, time administered: _____, dose _____ mg/kg
2. Tumor first visualized: _____
3. Did the contrast between the tumor and normal tissue **change after initial visualization of the tumor?**
No change in Contrast over Time / Increased Contrast over Time / Decreased Contrast over Time
4. If there was a change in contrast over time, **when did peak fluorescence** occur such that there was maximum contrast between the tumor and normal tissue? _____
5. Did the tissue become **saturated** with fluorescein such that there was no difference in the fluorescence of nerve and tumor? Yes / No
 - a. If so, when did saturation occur? _____
6. When did the fluorescence diminish such that it was no longer useful _____ / Not Applicable

For the following questions, please circle one number in the boxes below.

7. How well did fluorescence **correlate with your visual assessment** of the tumor and nerve tissue under normal microscopy without the Yellow 560 filter?

No correlation 1	Some correlation 2	Good correlation 3	Excellent correlation 4
---------------------	-----------------------	-----------------------	----------------------------

8. How well did fluorescence **correlate with electrostimulation** (e.g. tissues with high fluorescence do not stimulate, whereas nerve tissues with low fluorescence do stimulate)?

No correlation 1	Some correlation 2	Good correlation 3	Excellent correlation 4
---------------------	-----------------------	-----------------------	----------------------------

9. How helpful was the use of FS and Yellow 560 filter in.... (circle a rating for each row)

	Not helpful at all	Minimally helpful	Somewhat helpful	Very helpful	N/A
Distinguishing tumor from normal nerve	1	2	3	4	0
Preserving facial nerve function	1	2	3	4	0
Preserving hearing	1	2	3	4	0
Detecting residual tumor	1	2	3	4	0

10. Based on the use and performance of FS in this case alone, **how likely are you to use FS** in future cases involving this tumor type (excluding the research trial)?

Unsure 0	Plan to not use in any cases 1	Plan to use in select cases 2	Plan to use in the majority of cases 3	Plan to use in all cases 4
-------------	--------------------------------------	-------------------------------------	--	-------------------------------

Comments for the research team: _____

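### The only saturation item on the surgeon survey compares nerve with tumor, while the dosing rule acts on saturation of any normal tissue, so saturation of non-nerve tissue can go unrecorded

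*Protocol*

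**What the plan says.** **Dosing rule.** Protocol 3.6.11, step 3 starts at 1 mg/kg and allows changes after the first 3 cases. One trigger is saturation: "If saturation of normal tissue with fluorescence occurs, the dose may be decreased", or FS may be given earlier in later cases. The tissue named is normal tissue in general.

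**Survey.** In Appendix 3, item 5 is the only item that mentions saturation. It defines it as saturation "such that there was no difference in the fluorescence of nerve and tumor? Yes / No". Sub-item 5a asks for the time, but only after a yes. Item 3 concerns contrast between tumor and normal tissue after first view, with the options "No change in Contrast over Time / Increased Contrast over Time / Decreased Contrast over Time". Item 4 asks for the time of peak contrast, only if contrast changed. Item 6 concerns washout: "When did the fluorescence diminish such that it was no longer useful", with a not-applicable option.

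**Scope.** Hypothesis 12 in 3.4 expects "visual differentiation of tumor and surrounding structures and nerves using YE560", so it is not limited to nerve. Item 15 of the same section says that color analysis may be done "between the tumor and surround nerves or structures of interest for meningiomas, HNP, and HNS". Section 3.5 likewise allows structures other than the facial and cochlear nerves for the non-vestibular tumors. Section 3.2 describes a cited use of FS with this filter in meningioma, where the comparison was with brain and bone.

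**Use of the survey.** Section 3.1 makes optimum dose and timing a secondary objective, to be judged from performance reported on the surgeon surveys.

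**The concern.** Saturation is the sign in step 3 that the dose was too high or was given too late. The form intended to document dose performance records that sign for one tissue pair only. For a vestibular schwannoma with the facial or cochlear nerve exposed, nerve is the normal tissue that matters and the two definitions largely coincide. For a meningioma against brain or bone, or any case with no nerve in the field, they can part. The surgeon then has no accurate answer to item 5: *No* is literally true but hides the saturation, a blank is ambiguous, and neither leads to a time. When doses and injection times are later compared from the surveys, such a case could count as one without saturation.

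**Working it through.** No arithmetic applies. The check is to trace how each situation would be entered on items 3 to 6.

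| Situation | Item 3 | Item 4 | Item 5 / 5a | Item 6 |
|---|---|---|---|---|
| A. Steady, good contrast | No change | skipped | No / no time | Not applicable |
| B. Non-nerve tissue saturated from first view; nerve still distinct or not in view | No change | skipped | No or blank / no time | Not applicable |
| C. Non-nerve tissue saturates after first view; nerve still distinct or not in view | Decreased | time of peak | No or blank / no time | Not applicable |
| D. Washout | Decreased | time of peak | No / no time | time |
| E. Nerve saturated | depends on onset | depends on onset | Yes / time | Not applicable |

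1. **A against B.** With item 5 answered *No*, the rows are identical. Item 3 records the direction of change after first view, not whether contrast existed. Contrast that was absent from the start and contrast that was good throughout are both unchanged.
2. **C against A and D.** Items 3 and 6 together separate C from both. They do not identify saturation, because the same answers fit a partial fade that stayed useful. The time in item 4 is that of peak contrast, not of saturation.
3. **E.** Saturation that includes a visible nerve is captured and timed. The gap is therefore limited to non-nerve tissue.
4. **Items outside 3 to 6.** The item 9 row on distinguishing tumor refers to normal nerve. The item 9 row on residual tumor, item 10 on future use and the comments line could reflect a problem, but none asks about saturation or its time.
5. **Missing option.** Items 6 and 9 let the surgeon mark that the question does not apply. Item 5 does not, so a case with no nerve in view must be answered *No* or left blank.

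**The case against.** The strongest reply is that the uncaptured case is narrow and that other records cover it. Section 1.3 places all these tumors next to cranial nerves, so a nerve will often be in view. Under the initial protocol FS is given at tumor exposure, so saturation would usually develop after first view, where item 3 at least registers a loss of contrast. Section 3.6.9 plans a similar color analysis for the other tumor types, and 3.6.11 provides paired images at three stages and video throughout microscope use. Items 9 and 10 should also score lower when contrast is useless. All of this stands and keeps the point small. It does not remove it: these sources are indirect, and none is a direct report of saturation and its time, whereas 3.1 rests the objective on the surveys.

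It is also said that step 3 acts on surgeons' experience, not on item 5, so the two need not share a definition. That is right as far as conduct goes. A reader might infer that dosing decisions would be misdirected or patients put at risk. The documents do not support that: surgeons see the field, the change is discretionary, and the 500 mg cap and adverse event monitoring do not depend on item 5.

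A second tempting inference is that missed early saturation is likely, because 3.4 says the authors of a cited peripheral nerve sheath tumor series "found saturation of all tissues with 3-4 mg/kg dose within 18 seconds of administration" and adds "We suspect that the optimal dose will be 3-4 mg/kg" for this trial. The 500 mg cap would permit such doses in most adults (500 / 4 = 125 kg; 500 / 3 = about 167 kg). This does not support the gap. Saturation of all tissues includes nerve, so item 5 would record it whenever a nerve is in view. Nothing in the Protocol reports saturation of other tissue with nerve spared.

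**Conclusion.** The mismatch is real and minor. Item 5 under-records saturation when the relevant normal tissue is not nerve, or when no nerve is visible. If that saturation is present from first view, items 3 to 6 cannot tell it from steady contrast. If it comes later, the loss of contrast shows but is neither named as saturation nor timed.

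The effect is confined to the survey evidence for the secondary objective on dose and timing. The number of cases among the planned 90 cannot be estimated, since the Protocol gives neither a tumor mix nor how often a nerve is in view. The primary endpoint (item 10), safety monitoring and dosing in the room are unaffected.

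The conclusion rests on two assumptions: that surgeons answer item 5 as worded, and that meningioma, paraganglioma and non-vestibular schwannoma cases stay in the study, as 3.1, 3.5 and the inclusion criteria in 3.6.5 provide. Sections 3.6.7 and 7.2 still carry withdrawal wording that mentions vestibular schwannoma only. If that wording were followed, the gap would shrink to the few vestibular cases with no nerve in view or with other tissue saturated.

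**What to change.** Split item 5 of the survey into two lines: (a) nerve, and (b) other normal tissue or structure of interest, to be specified. Each line would read *indistinguishable from tumor: Yes / No / Not in field*, with a time if yes. Line (b) separates situation B from situation A, and the times locate the onset in B and C. Use the same definition of saturation in 3.6.11, step 3, so that the event that prompts a dose change is the event recorded. The decision on dose stays with the surgeons as now.

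The cost is one more survey line and a wording change in step 3, with no added procedure or staff. Surveys already completed would hold only the nerve answer. For those cases line (b) should be shown as not collected, not as *No*.
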